5.3 Secondary Efficacy Endpoints

The key secondary efficacy endpoints include the following:

- Mean change in Hb value between Baseline (mean pretreatment Hb) and the secondary evaluation period (Weeks 40-52)
- Proportion of subjects with Hb values within the target range during the primary evaluation period (Weeks 24-36)
- Proportion of subjects with Hb values within the target range during the secondary evaluation period (Weeks 40-52)

Other secondary efficacy endpoints include:

- Proportion of time with Hb values within the target range during the primary evaluation period (Weeks 24-36)
- Proportion of time with Hb values within the target range during the secondary evaluation period (Weeks 40-52)
- Proportion of subjects with Hb increase of >1.0 g/dL from Baseline
- Time to achieve Hb increase of >1.0g/dL from Baseline

- Mean change in Hb between Baseline (mean pretreatment Hb) and the primary evaluation period (mean Hb from Weeks 24-36) stratified by pre-baseline ESA exposure
- Progression of CKD
- Proportion of subjects receiving IV iron therapy from Baseline to Week 52
- Mean monthly dose of IV elemental iron administered from Baseline to Week 52 in subjects who have received IV iron
- ESA rescue
- Dose adjustments from Baseline to Week 52
- Proportion of subjects receiving RBC transfusion(s) from Baseline to Week 52

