If new elevations in ALT or AST >3 times ULN, **without** an elevation of total serum bilirubin >2 times ULN are identified, the following steps are to be taken:

- Temporary discontinuation of Investigational Medicinal Product (IMP);
- Repeat testing of ALT, AST, ALP, and total bilirubin, should be completed within 48 to 72 hours to confirm the abnormalities and to determine trend;
- IMP should not be resumed until monitoring indicates abnormalities have resolved or have stabilized.

Details on the management of subjects with other ALT and AST abnormalities are further described in [Section 9.4, Study Medication Stopping Rules](#).

Worsening of Anemia – In this study, it is possible that some subjects may experience a worsening of anemia. As the primary endpoint of this study assesses Hb response, worsening of anemia is captured as part of this efficacy parameter. Worsening of anemia should not be

considered an AE unless the worsening of anemia is associated with a cause *other than* the subject's CKD.

Transplantation – During this long-term study, it is anticipated that some subjects may receive a kidney transplant. These events will not be recorded as AEs. Subjects will discontinue study medication for receipt of a kidney, other solid organ, hematopoietic stem cell or bone marrow transplant and should continue with the Schedule of Activities and safety assessments as described in [Section 7.5.5.2, Permanent Discontinuation of Study Medication](#).

Malignancy – During this long-term study, some subjects may develop a newly diagnosed malignancy or a recurrence of a malignancy. At the discretion of the Investigator, these subjects may continue study medication (vadadustat or darbepoetin alfa). For reporting of adverse events of malignancy, see [Section 10.1.2 Serious Adverse Events](#).

Renal-Related Events - Some subjects will experience a progression of their CKD over the course of this study as part of the natural course of the disease. In addition, the study population is prone to experience acute, transient loss of kidney function of different etiologies, sometimes concomitantly complicated by progression of CKD.

To ensure consistent reporting of renal events, the following guidelines are to be used when reporting a renal-related AE:

- The following situations **should always be reported as SAEs** with seriousness criterion “medically important,” if no other seriousness criteria are met (see Section 10.1.2, Serious Adverse Events):

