 - **Progression of CKD leading to chronic dialysis**: When a subject undergoes transition to chronic maintenance dialysis, an SAE should be reported using the verbatim term of “end-stage renal disease” with the outcome denoted as recovered with sequelae of chronic dialysis.
 - **Any medical event requiring transient acute dialysis**: When a subject undergoes transient acute dialysis, an SAE should be reported using the verbatim term reflecting the indication for the dialysis. Examples of verbatim AE terms include: hyperkalemia, volume overload, acute kidney injury, and uremia.
 - **Kidney transplantation**: When a subject receives a kidney transplant, an SAE should be reported using the verbatim term “Progression of CKD,” with the outcome denoted as recovered with sequelae of “kidney transplant.”
- The following situations will be **reported as SAEs if they meet seriousness criteria** (see Section 10.1.2, Serious Adverse Events); otherwise, they should be reported as AEs:
 - **Acute kidney injury not requiring dialysis** – The reported AE term should reflect the etiology for the impairment of the renal function. Non-specific AE terms such as “Decreased eGFR” or “Increased creatinine” should be avoided whenever the underlying etiology is known.
 - Examples of verbatim AE terms for prerenal impairment include: hypovolemia, hepatorenal syndrome, and heart failure
 - Examples of verbatim AE terms for intrarenal impairment include: acute tubular necrosis, acute interstitial nephritis, and glomerulonephritis

- Examples of verbatim AE terms for postrenal impairment include: hydronephrosis, pelvicaliectasis, and urinary tract obstruction
- Progression of CKD not requiring dialysis – If permanent loss of renal function due to underlying CKD has occurred, the reported AE term should reflect the underlying etiology. Non-specific terms such as “Decreased eGFR,” “Increased creatinine,” or “Worsening CKD” should be avoided whenever the underlying etiology is known. Examples of verbatim AE terms include: worsening lupus nephritis, worsening diabetic kidney disease, and worsening glomerulonephritis.

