- Medical conditions related to CKD that occur without acute kidney injury or progression of CKD – If there is no decline in kidney function, the medical complication of CKD itself should be reported. AE terms such as “Progression of CKD” or “Acute Kidney Injury,” should be avoided when there is no decline in kidney function. Examples of AE terms include: edema and hyperkalemia.

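### Sections 10.1.1 and 10.1.2 give incompatible rules for reporting kidney transplants, and one of them files a transplant under a different term from progression to dialysis

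*Protocol*

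**What the plan says.** All references are to Amendment 7 (Version 8). The superseded protocol text in the same file is not used as evidence.

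**Whether a transplant is reported**
- Section 10.1.1, *Procedures*: procedures are not AEs, but the condition that led to them may be. Pre-planned procedures without new or worsening disease are not AEs either, and kidney transplant is named as the exception.
- Section 10.1.1, *Transplantation*: "These events will not be recorded as AEs".
- Section 10.1.1, *Renal-Related Events*: kidney transplantation is listed among situations that are always SAEs. The rule reads "When a subject receives a kidney transplant, an SAE should be reported using the verbatim term" *Progression of CKD*, with kidney transplant recorded as the outcome.
- Section 10.1.2: a transplant is classed as serious where it was immediate, that is, not pre-planned.

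**Which term is used (Section 10.1.1, *Renal-Related Events*)**
- Start of chronic dialysis is to be "reported using the verbatim term of “end-stage renal disease” with the outcome denoted as recovered with sequelae of chronic dialysis".
- For progression without dialysis: "If permanent loss of renal function due to underlying CKD has occurred, the reported AE term should reflect the underlying etiology". Non-specific terms are to be avoided if the cause is known.
- For complications of CKD without acute kidney injury or progression, the term *Progression of CKD* "should be avoided when there is no decline in kidney function".

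**How events are tabulated**
- Section 11.7.2 summarises numbers and percentages of subjects, by System Organ Class and Preferred Term, per arm. SAEs get their own summary.

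**The concern.** The renal rules are meant to make reporting consistent. They do not say with one voice whether a transplant is an adverse event, or when it is serious.

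The terms raise a second difficulty. Among the named renal situations, the words *Progression of CKD* are prescribed only for receipt of a graft, while progression to chronic dialysis goes to another term. Receipt of a graft depends on donor availability and waiting-list position as well as on disease. Both relevant cases are foreseeable: Section 7.3 (criterion 12) admits wait-listed subjects, and Section 7.5.2 keeps subjects in the study after they start chronic dialysis.

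At stake is the readability of the renal lines in the SAE tables. Someone comparing arms on a row labelled as CKD progression could be comparing mainly transplants, with a count that depends on which instruction each site followed.

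**Working it through.** The protocol states no figure on this point, so there is nothing to reproduce. The check sets the rules side by side and follows the counts in symbols.

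**Step 1. Can the rules all be followed at once?** Take a pre-planned transplant in a wait-listed subject.
- *Procedures* paragraph: reportable, because transplant is the named exception.
- *Transplantation* paragraph: not recorded as an AE.
- Always-SAE list: an SAE under *Progression of CKD*.
- Section 10.1.2: outside the class singled out as serious, because it was pre-planned.

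No single entry satisfies all four. Section 10.1.2 refers the reader to Section 10.1.1 for guidance, which leads back to the conflict.

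**Step 2. What do the tables show under each rule?** For one arm, let *D* be the subjects who start chronic dialysis, *B* those of the *D* who are later transplanted, *P* those transplanted without prior dialysis, and *u* the number of transplants that were not pre-planned (0 ≤ *u* ≤ *B* + *P*). Subjects with kidney failure number *D* + *P*. Assume that the two verbatim terms code to different Preferred Terms.

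| Rule followed | End-stage row | Transplants in the SAE *progression* row |
|---|---|---|
| Always an SAE | *D* | *B* + *P* |
| Serious only if not pre-planned (10.1.2) | *D* | *u* |
| Not recorded as an AE | *D* | 0 |

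The same patients contribute anything from 0 to *B* + *P* transplants to the SAE table.

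**Step 3. What does the term split do where the always-SAE rule is followed?**
- The end-stage row shows *D* and falls short of the kidney-failure count by (*D* + *P*) − *D* = *P*, the pre-emptive transplants.
- The progression row consists largely of transplants, because dialysis has its own term and progression of known cause is named by that cause. It need not be transplants only: progression of unknown cause may still carry a generic term.
- The *B* subjects appear once in each of two rows. Adding the rows gives *D* + *B* + *P*, which exceeds the subject count by *B*. Section 11.7.2 does not plan that sum. These subjects count once per row and once in the any-SAE total.

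**Step 4. What if the terms code to the same Preferred Term?** The shared row then holds *D* + *P* subjects under the always-SAE rule, and the split disappears. The conflict in Step 1 remains.

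**The case against.** **The two statements in Section 10.1.1 can be read together.** On this reading the transplant procedure is not an AE, and the underlying disease is reported with transplant as its outcome, in line with the convention on procedures. This is the best defence, and it also shows why making *kidney transplant* an AE term would be a poor remedy. But the text never says so, the exemption for pre-planned transplants points the other way, and neither the qualifier in Section 10.1.2 nor the difference in terms is explained.

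**The records stay separable.** The outcome must name dialysis or transplant, so an analyst can rebuild kidney failure per subject. That stands for transplants that were reported. It does not help with those left out under the not-an-AE rule, and the tables described in Section 11.7.2 are by term, not outcome.

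**Stronger readings that the documents do not support**
- *Every transplant must be reported as progression.* That is one of several conflicting instructions, not the settled rule.
- *Patients are counted twice.* The planned tables count subjects. Appearing in two rows for two distinct events is not in itself an error.
- *The advice to avoid the term when function has not declined flatly contradicts the transplant rule.* That bullet concerns complications such as edema. At most there is tension when a subject already on dialysis receives a graft and is filed as a new progression.
- *The secondary efficacy endpoint is distorted.* Section 5.3 lists "Progression of CKD", but nothing derives it from AE terms, and Section 9.2.2 collects serial eGFR.

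**Conclusion.** The point holds as a conflict in reporting rules with a secondary problem of terminology. Sections 10.1.1 and 10.1.2 cannot all be followed for a pre-planned transplant, so what reaches the SAE tables depends on which instruction a site applies. Where the always-SAE rule is applied, transplant and dialysis carry different terms for what is, in both cases, kidney failure.

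The size cannot be given. The protocol has no transplant or dialysis rates, so the effect can be stated only as a range: from none to all transplants in the SAE progression row, and an end-stage row short by the number of pre-emptive transplants. The row effects assume that the two terms code to different Preferred Terms, which the protocol does not state. Section 11.7.2 totals are not inflated.

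The rules apply to both arms alike, and no bias between arms is shown. No efficacy or MACE analysis is shown to depend on these terms. The importance is low, but the text is wrong as it stands and cheap to repair.

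**What to change.** Reconcile the *Procedures*, *Transplantation* and *Renal-Related Events* paragraphs of Section 10.1.1 with Section 10.1.2 so that one transplant rule remains:

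1. Report the underlying condition as *end-stage renal disease*, once per subject, at the first of chronic dialysis or transplant, with dialysis or transplant recorded as the outcome. A transplant after dialysis is added to the existing record rather than filed as a new event. This keeps the convention that procedures are not AEs.
2. Do not use *Progression of CKD* for a transplant unless a new loss of kidney function is documented.
3. State once whether a pre-planned transplant is covered and whether it is serious, with the same wording in both sections.
4. In Section 11.7.2, add a summary of kidney failure per subject (first chronic dialysis or transplant) by arm.

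Cost: amendment wording, CRF completion guidance, and recoding of existing transplant records. No new data are needed for transplants already recorded. Sites that followed the not-an-AE rule would have to be asked about transplants they left out.

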4.3 Potential Benefits and Risks

Please see the vadadustat Investigator's Brochure for additional discussion and information for the following section.

Trials of injectable erythropoiesis-stimulating agents (ESAs) in patients with anemia secondary to NDD-CKD or DD-CKD have demonstrated an increased risk of cardiovascular events associated with higher Hb targets (Besarab 1998; Singh 2006; Pfeffer 2009). Post-hoc analyses performed by the FDA and others have shown an association between these adverse outcomes and supraphysiologic serum EPO levels and/or Hb oscillations and overshoots (McCullough 2013, Unger 2010). In studies to date, oral vadadustat daily increased mean Hb with few excursions above the target range. In addition, serum EPO levels remained well below those

reported with ESAs in the literature. As a result, there is the potential for the investigational drug vadadustat to provide an effective and safe therapeutic option for the treatment of renal anemia.

In addition, vadadustat may enhance iron metabolism and transport. Phase 1 and Phase 2 trials have demonstrated a consistent dose-dependent increase in TIBC and decrease in ferritin and hepcidin. Mechanistic studies have demonstrated that HIF stabilization downregulates the iron absorption regulator hepcidin, and upregulates the iron-mobilizing regulators ferroportin and transferrin (and its receptor) (Peyssonnaud et al. 2007). Potential clinical benefits include enhanced erythropoiesis and decreased exogenous iron requirements.

The toxicological profile of vadadustat supports continued development in the ongoing Phase 3 clinical trials. Dose-limiting toxicity noted in the exploratory toxicology studies was due to hemoglobinuric nephropathy (rat) and emesis associated with body weight loss (dog). Dose-limiting toxicity noted in the sub-chronic and chronic toxicology studies was due to exaggerated pharmacology and the sequelae of events related to polycythemia (increased RBC mass, blood hyperviscosity and fibrin thrombi); polycythemia-related toxicity was consistent across species, monitorable and reversible. In the completed clinical studies, vadadustat has had an acceptable safety profile to support further development.

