11.7.2 Analysis of Adverse Events

Adverse events will be summarized using the number and percentage of subjects with AEs for all subjects in the safety population. Summaries will also be provided for subgroups including Region, Age, Gender and Race.

All AEs will be coded using MedDRA. Treatment-emergent and post-treatment AEs will be summarized by System Organ Class and Preferred Term for each treatment group. Adverse events will also be summarized by their maximum severity.

Summaries will also be provided for the following types of AEs:

- SAEs
- Related AEs (including all categories for relationship to study medication other than “Unrelated”, as determined by the Investigator)
- AEs leading to early discontinuation of study medication

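### Acute kidney injury of known prerenal or postrenal cause is reported under its cause alone, so the adverse event tables will understate it

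*Protocol*

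**What the plan says.** All references are to the protocol, Amendment 7.

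The Renal-Related Events part of section 10.1.1 sets three rules that matter here; its stated aim is consistent reporting.

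- **AKI not requiring dialysis.** "The reported AE term should reflect the etiology for the impairment of the renal function". For prerenal causes: "Examples of verbatim AE terms for prerenal impairment include: hypovolemia, hepatorenal syndrome, and heart failure". For intrarenal causes: "Examples of verbatim AE terms for intrarenal impairment include: acute tubular necrosis, acute interstitial nephritis, and glomerulonephritis". For postrenal causes: "Examples of verbatim AE terms for postrenal impairment include: hydronephrosis, pelvicaliectasis, and urinary tract obstruction". Decreased eGFR and increased creatinine are to be avoided as terms when the etiology is known.
- **Events requiring transient acute dialysis.** These are always serious, and the term is the indication for dialysis: "Examples of verbatim AE terms include: hyperkalemia, volume overload, acute kidney injury, and uremia".
- **CKD-related conditions without decline in kidney function.** "Examples of AE terms include: edema and hyperkalemia". The AKI term is discouraged here because function has not declined.

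Section 11.7.2 then states: "Treatment-emergent and post-treatment AEs will be summarized by System Organ Class and Preferred Term for each treatment group". It adds summaries by severity, seriousness, relatedness, discontinuation and subgroup.

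Earlier in section 10.1.1, an accident caused by a medical condition is handled differently: the fall and the dizziness behind it are reported as two events.

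**The concern.** An adverse event table can count only what the reported term names. If a site follows the non-dialysis rule for an AKI caused by volume depletion, cardiac decompensation or obstruction, the kidney injury need not appear in the term at all. The entry then looks the same as hypovolemia, heart failure or obstruction in a patient whose kidney function did not change.

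Section 10.1.1 itself describes this population as prone to acute, transient loss of kidney function, so AKI is an event that readers of the safety comparison will look for. Relatedness is also judged per adverse event (section 10.3.5). For such an episode, the recorded judgement would concern the heart failure or the hypovolemia, not the kidney injury.

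**Working it through.** No power, alpha or event count is involved, and the protocol states no AKI rate. The check is a comparison of the reporting rules with the tabulation rule and the laboratory schedule.

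**1. Which non-dialysis example terms keep the kidney injury visible?**

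| Group | Kidney diagnosis in the term | Term equally usable without kidney injury |
|---|---|---|
| Prerenal | hepatorenal syndrome | hypovolemia, heart failure |
| Intrarenal | acute tubular necrosis, acute interstitial nephritis, glomerulonephritis | none |
| Postrenal | none | hydronephrosis, pelvicaliectasis, urinary tract obstruction |

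Four of nine stay recognisable (1 + 3 + 0) and five of nine do not (2 + 0 + 3). This counts examples, not events. One of the four is weaker than it looks: glomerulonephritis reappears, with the word worsening in front, as an example for chronic progression.

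**2. Can the tables separate the two uses?** For the five terms, no. The severity, seriousness, relatedness and subgroup summaries in section 11.7.2 are built from the same terms. A grouped renal search in the SAP cannot find AKI inside an entry that reads only hypovolemia.

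**3. Hyperkalemia.** It is an example indication for acute dialysis and also an example for events without decline in kidney function. The dialysis case is always serious. The other case becomes serious whenever it meets an ordinary criterion, such as hospitalization. Seriousness therefore separates the two only in part.

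**4. Can the laboratory data fill the gap?** Central creatinine is scheduled as follows (sections 9.2.2, 9.3.5, 9.3.7, 9.3.8):

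- Year 1: Weeks 4, 8, 12, 20, 28, 36, 44 and 52, so gaps of 4 to 8 weeks.
- Afterwards: Weeks 76, 104, 128, 156, 180 and 208, so gaps of 24 or 28 weeks (76 − 52 = 24; 104 − 76 = 28; and so on).
- A fall in eGFR of at least 50% prompts a repeat after 30 to 60 days, which tests persistence rather than a transient episode.

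An episode that begins and resolves between visits is seen only if it is reported as an adverse event.

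**5. Direction of the error.** Let a share m of AKI be masked in each arm, with one episode per patient. Observed incidence is then (1 − m) times true incidence. The between-arm difference shrinks by the same factor and the ratio is unchanged. If the mix of causes differs between arms, m differs too, and the ratio can move either way.

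**The case against.** The strongest reply is that the rule is softer than it looks. The term should reflect the etiology, so an entry such as prerenal AKI due to hypovolemia would arguably comply. The terms to avoid are non-specific laboratory ones, and AKI is discouraged only where function has not declined. The rule is the same in both arms. All of this is correct, and it means that masking is likely rather than certain. But AKI is not among the nine examples for this category, and sites follow examples. A separate laboratory entry is not a reliable substitute: section 10.1.1 sends abnormalities tied to an already reported event to the comments field.

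Several stronger readings are tempting, and the protocol does not support them.

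- **AKI vanishes from the tables.** It does not. It is an allowed term for acute dialysis, and four of the nine non-dialysis examples are kidney diagnoses.
- **AKI is reported as hyperkalemia under the non-dialysis rule.** Hyperkalemia is not an example there.
- **The heart failure endpoint is affected.** That endpoint is hospitalization for heart failure, adjudicated by a blinded committee (section 6.5). Only the adverse event tables are mixed.
- **The data monitoring committee sees only masked tables.** It also reviews laboratory data (section 6.4.2).
- **A nonclinical kidney finding would be hidden.** Section 4.3 names hemoglobinuric nephropathy in rats as dose-limiting in exploratory studies. Direct kidney toxicity of that kind would be expected to be intrarenal, where the terms stay visible. In longer studies the dose-limiting toxicity was related to polycythemia.
- **A loss of statistical sensitivity can be quantified.** No AKI rate is given, and section 11.7.2 plans descriptive summaries without a test.

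**Conclusion.** The point holds in limited form. For AKI not requiring dialysis, with a known prerenal or postrenal cause, following section 10.1.1 as illustrated puts the event under a term shared with the same condition without kidney injury. The Preferred Term count will then understate AKI. The SAP cannot repair this, because the information is lost at data entry, and scheduled creatinine recovers transient episodes only in part. The double use of hyperkalemia is a smaller inconsistency in the same section.

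The extent is five of nine example terms; the number of patients is unknown. The conclusion assumes that sites follow the examples and that a meaningful share of AKI in this population has a known prerenal or postrenal cause. It does not touch the efficacy analyses, MACE or the adjudicated endpoints. A correction is worth making because it is cheap and improves the between-arm safety comparison.

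**What to change.** Reword section 10.1.1 and the CRF guidance as follows.

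1. Any adverse event that the investigator judges to be AKI is reported with acute kidney injury as an adverse event term, with or without dialysis.
2. The etiology is reported as a second event when it is itself an adverse event, as the same section already does for a fall and dizziness. The list of plausible causes in section 10.3.5 should not be used for this. It is an optional attribution list with categories such as medical history and study medication, and an etiology fits only under its open category.
3. The hyperkalemia examples are reconciled, so that an event needing acute dialysis can be told apart from one without decline in kidney function.

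Apply this going forward. Any query of terms already entered should be triggered by prespecified central creatinine criteria applied blind to arm. In an open-label trial, free re-labelling by sites could be influenced by knowledge of treatment. Such queries reach only episodes visible in central samples.

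The cost is the rewording, some additional adverse event entries and a limited query round. No new study procedure is needed.
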